The study will use a randomized-experimental design and will be randomized via envelope randomization, with experimenters being blinded. A total of 104 patients, 26 in each group, will undergo initial incentive spirometry and force vital capacity (FVC) and FEV₁ tests. Groups will consist of a control versus experimental group, stratified into bilateral and unilateral rib fractures. Three days' worth of data will be collected for each of the tests and will also be collected 24 hours prior to discharge. Length of stays will be compared for experimental and control groups, as well as time to ambulation (collected from the first physical therapy assessment). Injury severity score will also be collected to determine any correlation by severity of injury. Patient satisfaction surveys for the device will also be collected to determine if the patients feel a difference with the device.

4) Background/Scientific Rationale and Significance

Little research as been conducted to determine the significance of a splinting device used in patients with chest trauma, and it is still uncertain whether these devices improve overall patient outcomes. Contradicting studies with similar experimental designs show either some significance (p-value) or insignificance in pulmonary function pre- and post-treatment. This gap in current knowledge leaves room for concern in whether the patient truly benefits from a splinting device in this type of injury. Changes in percent predicted FVC/FEV₁ ratio in this patient population are not readily demonstrated in most of these studies, as well as differing length of stays. This study will contribute to this base of knowledge by determining the effects of the Duracore splinting device on this patient population using the objectives.

5) Inclusion and Exclusion Criteria

Inclusion:

- Adult patient admitted to the trauma service at Penrose Hospital
- Willing and able to comply with all requirements of the study
- Active diagnosis of rib fractures
- Male or female ages 18 and older
- Able to provide written informed consent to participate in the study
- Must be physically able to don and use the splinting device independently without assistance

Exclusion:

- <18 years old
- History of pulmonary disease, lobectomy, or lung transplant
- Current smoker of tobacco products >5 years
- Diagnosis of flail chest

- Pregnant Women
- Prisoners
- Cognitively Impaired; must be alert and oriented x 3

6) Number of Subjects

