Number of subjects was based on a power analysis using FVC/FEV₁ as the primary variable and stratified by unilateral versus bilateral diagnosis. Previous literature suggests a standard deviation of approximately 0.20-0.60 for FVC/FEV₁ values. SD was set at 0.40. Unilateral control was estimated to be 50% of predicted values (FVC/FEV₁) due to the nature of the injury, set at approximately 1.50L, with bilateral set at approximately 1.35L. Unilateral experimental group means were increased by 20% of predicted values to 1.80L, and bilateral to 1.50L. The required sample size to achieve 80% power to detect difference between splint and control groups is 104, with each group requiring 26 subjects each. Power calculations were performed in R version 4.0.0 with the pwr2ppl package, using the anova2x2 function.

Number of subjects to be used are 150 to account for withdrawals, incomplete data sets, extraneous results, etc. This is a single site study.

7) Recruitment Methods

Respiratory Therapy is part of the trauma multi-disciplinary team. and is involved with the care of every trauma patient admitted to Penrose Hospital. During trauma rounds in the ICU and floor patients that met criteria for the study will be identified. The investigators will approach those identified patients for potential enrollment in the study. Note they will not approach any patient for consent that is under their care that shift. There are no flyers or advertisements for this research or device.

8) Study Timelines

It is estimated that it will take at least one year to complete this study to include enrollment, subject completion, and all analysis. All primary variables and analyses should be completed by this time.

9) Study Endpoints

The primary endpoint of this study is to investigate the use of the Duracore splinting device in patients with chest trauma. Hospital length of stays, time to ambulation, a patient satisfaction survey, incentive spirometry, forced vital capacity measurements, and the injury severity score will be correlated to a control group to determine its' effectiveness. The quantitative data points will be collected over the first three days of hospital stay and 24 hours prior to discharge. The qualitative data will be collected prior to patient discharge. The hypothesis of this study is that the use of the Duracore splinting device will reduce hospital length of stays and improve patient lung capacities over the course of admission following chest trauma.

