The design of this study is a randomized experimental trial. The procedures involved in this study will first include obtaining the individual's consent to participate. Incentive spirometry is a standard of care that has been proven to improve deep breathing for patients. FVC/FEV₁ measurements are not always routinely done at this site but has been proven to be an indicator in respiratory deterioration in this population. Enrollment of each subject will be on a one to one basis for control and experimental groups. The trial will be randomized to reduce bias by randomly selecting patients between control and experimental groups by alternating every other patient receiving the treatment. Height, sex, ethnicity, and age will be accounted for as well to calculate the percent predicted FVC/FEV_1 to reduce statistical error. Enrollment will be based on patient consent. After enrollment into the study after admission to the hospital, baseline values of incentive spirometry (IS) and spirometry will be done. The patient will then be placed in the experimental or control group after being assigned a group via envelope randomization. If the patient is under experimental, they will receive a splinting device for treatment. Control groups will receive standard of care treatment without the splinting device. Continued analysis of IS and FVC/FEV₁ will occur over three days, and a final collection prior to discharge. Discharge planning will be coordinated with respiratory therapy, so the patient does not go home without completing the survey and final analysis. The patient satisfaction survey will be a paper survey administered to the patient. Patient identifying information will not be present on this form to maintain confidentiality. The patient will be asked if they would like to complete the form and that it is an anonymous short survey to help with identifying how the patient felt about the research. The subject will only be enrolled in the study for the duration of their hospital stay as an inpatient. There will be no follow-up after discharge, and any patients who are discharged without completing the final analysis will be omitted from the study.

11) Data Analysis Plan

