Data analysis will include a two-tailed t-test to account for significance between control and experimental groups. This will be done with both incentive spirometry and FVC/FEV₁. Correlations will be made with time to ambulation and length of stays, as well as injury severity score. Graphic representation of trends will also be used to demonstrate differences between the groups. Qualitative analysis will include providing averages from the questionnaire using a Likert scale. These averages will be used to determine whether the population felt the device provided any help with their chest trauma. Number of subjects was based on a power analysis

using FVC/FEV₁ as the primary variable. Previous literature suggests a standard deviation of approximately 0.20-0.60 for FVC/FEV₁ values. SD was set at 0.40. Unilateral control was estimated to be 50% of predicted values (FVC/FEV₁) due to the nature of the injury, set at approximately 1.50L, with bilateral set at approximately 1.35L. Unilateral experimental group means were increased by 20% of predicted values to 1.80L, and bilateral to 1.50L. The required sample size to achieve 80% power to detect difference between splint and control groups is 104, with each group requiring 26 subjects each. Power calculations were performed in R version 4.0.0 with the pwr2ppl package, using the anova2x2 function. Number of subjects to be used are 150 to account for withdrawals, incomplete data sets, extraneous results, etc. This is a single site study.

Patient satisfaction surveys will use a numbered Likert Scale. The averages of each answer will be used to reinforce the efficacy of the device and correlate to primary data. Randomization will occur by experimenter-blinded envelope randomization.

12) Provisions to Monitor the Data to Ensure the Safety of Subjects

Subjects will be monitored for the duration of their stay by all staff members, and any adverse events related to the device itself will be reported accordingly. This device claims minimal risk to patients due to its unrestrictive and non-invasive nature but will be monitored by investigators for any adverse effects. **The Data Safety Monitoring staff will review all documentation accordingly at least quarterly.**

13) Withdrawal of Subjects

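### Section 9 lists the injury severity score, which reflects injury before assignment, among the effectiveness measures, and section 11 does not use it as a covariate

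*Combined protocol and SAP*

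**What the plan says.** The combined protocol and SAP gives the injury severity score different roles in different places.

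- Section 9 (Study Endpoints) names it in one sentence with length of stay, time to ambulation, the satisfaction survey, incentive spirometry and FVC. The sentence says that these and "the injury severity score will be correlated to a control group", and gives the purpose as judging whether the device is effective. The only timing given there is common to all quantitative data: "The quantitative data points will be collected over the first three days of hospital stay and 24 hours prior to discharge". The score has no baseline timing of its own.
- Section 3 (Objectives and Hypothesis(es)) gives it a descriptive purpose: "Injury severity score will also be collected to determine any correlation by severity of injury".
- Section 11 (Data Analysis Plan) mentions it only here: "Correlations will be made with time to ambulation and length of stays, as well as injury severity score".

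The one between-arm test that is named is unadjusted: "Data analysis will include a two-tailed t-test to account for significance between control and experimental groups". Section 11 applies it to incentive spirometry and FVC/FEV₁. The variables that the plan does account for are others. Section 10 says "Height, sex, ethnicity, and age will be accounted for as well to calculate the percent predicted" values, and section 3 has the groups "stratified into bilateral and unilateral rib fractures". Nowhere is the severity score a covariate, a stratification factor or a variable to be checked for balance.

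**The concern.** An effectiveness measure has to be something that the device could change. A severity score describes the injury that brought the patient to hospital, and the splint is given afterwards. If the arms differ in it, the explanation is chance, the way patients were allocated, or which patients remained in the analysis. Section 9, read as written, offers such a difference as evidence on the device.

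The second half of the concern is lost information. Length of stay and lung function are the two parts of the hypothesis, and both plausibly depend on how badly the patient was hurt. The score is already on the list of variables to be collected, yet no between-arm comparison uses it. If the decision to adjust is left until outcomes are known, it becomes a post hoc choice.

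**Working it through.** **1. Can the splint change the score?** Section 3 describes the score as a measure of severity of injury. Section 10 gives the order of events: admission, consent, baseline incentive spirometry and spirometry, then assignment, then the splint or standard care. The injury precedes every step. The documents do not say when the score is calculated, but what it measures is fixed before assignment.

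**2. Reproducing the planned sample size.** Inputs from section 6: SD 0.40; control means 1.50 (unilateral) and 1.35 (bilateral); experimental means 1.80 and 1.50; 26 per cell, N = 104; 80% power. Alpha is not stated, so I take 0.05 two-sided.

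- Average splint effect: δ = [(1.80 − 1.50) + (1.50 − 1.35)]/2 = (0.30 + 0.15)/2 = 0.225.
- Main effect in a 2×2 ANOVA: non-central F with 1 and N − 4 degrees of freedom, λ = N(δ/2)²/SD².
- N = 104: λ = 104 × 0.1125²/0.16 = 8.23, power 81.1%.
- N = 100: λ = 7.91, power 79.5%.

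So 104 is the smallest balanced total that reaches 80%, and the plan's figure is reproduced. A normal approximation with 52 per arm gives 81.8%.

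**3. Adding the score as a covariate.** Let r be the within-cell correlation between score and outcome. The residual SD becomes 0.40√(1 − r²), λ becomes 8.23/(1 − r²), and the error degrees of freedom fall from 100 to 99. The documents give no value for r, so every row is an assumption.

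| r (assumed) | Residual SD | λ at N = 104 | Power at 26 per cell | Smallest balanced N for 80% |
|---|---|---|---|---|
| 0 | 0.400 | 8.23 | 81.1% | 104 |
| 0.1 | 0.398 | 8.31 | 81.5% | 104 |
| 0.2 | 0.392 | 8.57 | 82.6% | 100 |
| 0.3 | 0.382 | 9.04 | 84.6% | 96 |
| 0.4 | 0.367 | 9.79 | 87.3% | 88 |
| 0.5 | 0.346 | 10.97 | 90.7% | 80 |

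A useless covariate (r = 0) costs nothing visible at one decimal place. The table is for the score alone. Once baseline spirometry is also in a lung-function model, the relevant r is the correlation that remains after it, which may be smaller.

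**4. How much chance imbalance to expect.** With 52 per arm, the difference in mean score, in SD units, has standard error √(2/52) = 0.196. P(|difference| > 0.3 SD) = 2[1 − Φ(0.3/0.196)] = 2[1 − Φ(1.53)] = 0.126. This is ordinary sampling variation under sound randomisation.

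**The case against.** The strongest reply is that the endpoint half rests on one badly built sentence. Section 3 names what is compared between arms (length of stay and time to ambulation) and keeps the severity score separate as a descriptor. The hypothesis restated in section 9 itself contains only length of stay and lung capacities, and section 11 plans no between-arm test of the score. This stands. A reader might infer from section 9 that the trial will test the score as an outcome and could claim benefit from it, but the rest of the plan does not support that. The fault is an inconsistency between sections, and section 9 is the one to correct.

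The second reply is that an unadjusted comparison is valid under sound randomisation, because chance imbalance is already covered by the type I error rate. This also stands. A reader might infer that leaving the score out biases or confounds the length-of-stay comparison; omission alone does not do that. Section 10 does describe giving treatment to alternate patients as well as envelopes, and it drops patients discharged before the final measurements. Either could make the analysed arms differ in severity by more than chance. That is a reason to report the score by arm, but it is a separate defect that a covariate does not repair.

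Third, the gain may be small. Eligibility excludes flail chest and cognitive impairment and requires patients to put the device on unaided, which may narrow the severity range and weaken r. At r = 0.1 or 0.2 power rises only to 81.5% or 82.6%. For lung function, the spirometry value taken before assignment is the more obvious covariate. Both points are accepted: the table starts at zero, and the fix includes baseline spirometry.

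What the reply does not remove is the section 9 wording, or the fact that section 11 leaves a collected prognostic variable out of every between-arm comparison.

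**Conclusion.** The point holds as a correction of the score's role and as an improvement in precision and balance. It is not a validity correction. The score belongs with the baseline characteristics, because a difference between arms in it cannot show a device effect.

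The size depends on a correlation that the documents do not give. On the planned FVC/FEV₁ comparison, with 26 per cell and alpha 0.05 two-sided assumed, power goes from 81.1% at r = 0 to 84.6% at r = 0.3 and 90.7% at r = 0.5. N = 104 is sufficient throughout. A reader might expect a larger, quantified gain for length of stay, but the documents give no variability, test or power for it, so no such figure can be supported. The baseline of 81.1% is for the 2×2 analysis used in section 6; section 11 names only a t-test.

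**What to change.** **Section 9.** Take the injury severity score out of the effectiveness list. List it as a baseline characteristic, state when it is scored, and report it by arm.

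**Section 11.** Prespecify the score and the unilateral/bilateral stratum as covariates in the between-arm models for length of stay, time to ambulation and lung function. In the lung-function models, add the spirometry value taken before assignment. State the type of model for length of stay and time to ambulation, since section 11 now gives only correlations for them.

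**Cost.** No new data: the score and baseline spirometry are already collected, and the sample size stays at 104. The score uses about one degree of freedom. Replacing t-tests with adjusted models is slightly more analysis work, and the change needs a written amendment with IRB approval, preferably before outcomes are examined. The allocation method in section 10 has to be resolved separately.

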splinting device is to be non-significant device. It is low risk and does not present potential for serious risk to the health, safety, or welfare of a subject. FDA recommendations are being followed to label the device accordingly. A nonsignificant risk device study requires only IRB approval prior to initiation of a clinical study. Sponsors of studies involving nonsignificant risk devices are not required to submit an IDE application to the FDA for approval per FDA regulations. The plan is to comply with the abbreviated IDE requirements under §812.2 (b):

The device will be labeled with "CAUTION – Investigational Device.
Limited by Federal (or United States) law to investigational use."
This is the current label for the device

• Will monitor for any adverse effects daily with subjects using the device 33) Other Requirements

REGULATORY, ETHICAL AND LEGAL OBLIGATIONS

Institutional Review Boards/Ethics Committees

• Before implementing this study, the protocol and all associated documents must be reviewed by a properly constituted committee or committees responsible for approving clinical studies. The IRB's written, signed approval letter must contain approval of the designated investigator(s) and the protocol (identifying protocol title, date and version number).

• Any change or addition to the protocol can only be made in a written protocol amendment that must be approved by the responsible party and the local IRB.

Patient Confidentiality and Disclosure

• Data on patients collected on eCRFs during the trial will be documented in an anonymous fashion and the patient will only be identified by the patient enrollment number, and by his/her initials. If, as an exception, it is necessary for regulatory reasons to identify the patient, all parties are bound to keep this information confidential.

• The investigator will guarantee that all persons involved will respect the confidentiality of any information concerning the study patients. All parties involved in the study will maintain strict confidentiality to assure that neither the person nor the family privacy of a patient participating in the trial is violated. Likewise, the appropriate measures shall be taken to prevent access of non-authorized persons to the study data.

Collection, Monitoring and Auditing Study Documentation, and Storage

Collection of Data and Monitoring Procedures

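### Section 10 gives two incompatible assignment rules, alternation and envelopes; if alternation is followed, the recruiting investigators could know almost every next assignment in advance.

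*Combined protocol and SAP*

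**What the plan says.** Section 10 (Procedures Involved) describes the allocation twice. First it says bias is reduced by "randomly selecting patients between control and experimental groups by alternating every other patient receiving the treatment". Later in the same paragraph, after consent and baseline spirometry, it says: "The patient will then be placed in the experimental or control group after being assigned a group via envelope randomization".

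The envelope rule also appears in the design paragraph of section 3, where the trial "will be randomized via envelope randomization, with experimenters being blinded", and in section 11: "Randomization will occur by experimenter-blinded envelope randomization".

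No section says which rule governs, how the order inside the envelopes is produced, who prepares or holds them, or whether they are numbered, opaque and sealed.

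Four other statements bear on the consequences:

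- Section 7, on recruitment: "The investigators will approach those identified patients for potential enrollment in the study".
- Section 12 says the device "will be monitored by investigators for any adverse effects". Section 26 adds, without naming who does it: "Will monitor for any adverse effects daily with subjects using the device".
- Section 5 includes an entry criterion that calls for judgement: "Must be physically able to don and use the splinting device independently without assistance".
- Section 10 gives controls standard care with no splint and mentions no sham.

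**The concern.** Alternation fixes every assignment after the first. Anyone who knows the rule and the last assignment knows the next one before approaching a patient. An envelope hides this only if its contents are in random order, and the only account the protocol gives of how the order arises is the alternation sentence.

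The people who recruit are placed to know the last assignment. The investigators monitor device effects, section 18 makes them the only collectors of chart data, and a patient with a splint is visibly in the experimental group. With the next arm known, an investigator could choose whom to approach first, decide not to approach, or apply the criterion on donning the device more or less strictly. None of this need be deliberate.

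Selection of this kind occurs before any data are analyzed. The main comparison in section 11 is a two-tailed t-test with no stated baseline or covariate adjustment, and it cannot tell a device effect from a difference in who was enrolled. A trial run by alternation could not be reported as randomized with concealed allocation. If instead the envelopes hold a random sequence, the protocol misdescribes its own method.

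**Working it through.** **Inputs from the protocol.** 150 patients to be enrolled and 104 required, 26 in each of four groups, so 52 per arm (sections 3 and 6); 1:1 allocation (section 10); two strata, unilateral and bilateral (section 3); SD 0.40 L and group means 1.50, 1.35, 1.80 and 1.50 L (section 6); two-tailed t-test (section 11).

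**Assumed, because the protocol does not give them.** Alpha 0.05, the size of any steering shift, and an even split between strata where one is needed.

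**1. The plan's own sample size.** The average treatment difference is (0.30 + 0.15)/2 = 0.225 L. For the treatment main effect in a balanced 2x2 ANOVA, the noncentrality is λ = N(0.225/2)²/0.40². At N = 104, λ = 8.23 and power is 81.1%. At N = 100, power is 79.5%. So 26 per group is the smallest size reaching 80%, and 104 reproduces. It does not depend on the assignment rule; what is at issue is bias, not a wrong N.

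**2. Predictability under alternation.** With one list, all assignments but the first are certain: (150 − 1)/150 = 149/150 = 99.3%. With one list per stratum, all but two are: 148/150 = 98.7%. Counting half a correct guess for the first patient on a single list, guess accuracy is g = 149.5/150 = 0.997.

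**3. Predictability under a random alternative.** The comparator, which the protocol does not mention, is permuted blocks of 4 and 6 mixed with equal odds.

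- Expected correct guesses in a block of 2m, with its size known, are m + (4^m/C(2m,m) − 1)/2.
- For m = 2: 2 + (16/6 − 1)/2 = 2.833 of 4.
- For m = 3: 3 + (64/20 − 1)/2 = 4.1 of 6.
- Together: 6.933/10 = 69.3%.
- In simulation, with 75 patients per stratum and an observer who knows the sizes used but not their order, 5.6% of assignments are certain (0.056 × 150 ≈ 8 patients) and 69.0% are guessed correctly.
- Simple randomization gives 50%.

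**4. Illustrative effect on the t-test.** Suppose the device has no effect and steering makes the arms differ in prognosis by δ SD. With n per arm, the two-sided rejection rate comes from the noncentral t with 2n − 2 degrees of freedom and noncentrality δ√(n/2).

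Steering bias is proportional to 2g − 1. The same effort under mixed blocks therefore gives (2 × 0.693 − 1)/(2 × 0.997 − 1) = 0.389 of the shift under alternation. With n = 52:

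| Shift under alternation | False-positive rate | Shift under mixed blocks | False-positive rate |
|---|---|---|---|
| 0.1 SD (0.04 L) | 8.0% | 0.039 SD | 5.4% |
| 0.2 SD (0.08 L) | 17.3% | 0.078 SD | 6.8% |
| 0.3 SD (0.12 L) | 32.9% | 0.117 SD | 9.1% |

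If all 150 patients were analyzed (75 per arm), the rates under alternation would be about 9%, 23% and 45%. The number 52 is used because it is the size the power calculation requires.

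**The case against.** **Envelopes look like the intended method.** They appear three times, twice described as blinded to experimenters, and in section 10 they are the operational step. Alternation appears once, just after the sentence on one-to-one enrollment, and may be a loose way of describing that ratio. This is a fair reading of intent, but it does not remove the conflicting sentence. Nor does it say how the envelopes are ordered; filling them alternately would satisfy both statements and remain predictable.

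**Some text limits steering.** Section 7 bars investigators from approaching patients under their own care that shift. Section 25 has consent obtained within 24 hours of admission. Sections 7 and 26 have eligible patients identified on trauma rounds or notified by the trauma team or respiratory therapy. These provisions narrow the room to act on a known assignment. They do not hide it, and the order of approach, or no approach at all, remains open.

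**Knowledge of the last assignment is partly inferred.** The daily-monitoring line in section 26 names no one, section 12 also involves all staff, and no shared enrollment log is described. It follows that not every investigator would necessarily know the latest assignment. Even so, section 12 names investigators as monitors of device effects, section 18 gives them sole charge of chart collection, and the splint is visible.

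**The bias figures are not evidence about this trial.** That is correct. The shifts and alpha are assumed and the block design is only a comparator. Only the 149 (or 148) of 150 follows from the protocol's own rule.

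**Conclusion.** The concern holds, and the protocol must be corrected. Section 10 contains, in current text, two assignment rules that cannot both be random, and no section resolves them. Under one of them, allocation is deterministic for 149 of 150 patients, or 148 with separate lists by stratum. That result rests only on the stated rule and the planned enrollment.

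The documents do not show that alternation will be used, and they give no basis for estimating how much bias would follow. The 8% to 33% false-positive rates are conditional on assumed shifts of 0.1 to 0.3 SD, alpha 0.05 and 52 per arm; they show that modest steering would matter, not that it will happen. The conclusion does not depend on them, since a predictable sequence is a defect whatever use is made of it.

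**What to change.** Delete the alternation sentence and state one method, in matching words, in sections 3, 10 and 11:

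- A computer-generated random sequence, separate for unilateral and bilateral fractures, prepared by someone not involved in recruitment. Permuted blocks of varying, undisclosed size are one acceptable choice. Simple randomization within strata is less guessable but less balanced.
- Assignments in sequentially numbered, opaque, sealed envelopes, one set per stratum, opened only after consent, confirmation of eligibility and baseline spirometry.

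This conceals the assignment until it is made. It does not blind staff afterwards, because controls have no sham device. The statements in sections 3 and 11 that experimenters are blinded should therefore say who is blinded and to what.

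The cost is one rewritten paragraph, conforming edits in two other sections, and two sets of envelopes prepared in advance. No extra patients or visits are needed.
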